## DOCUMENT HISTORY

VERSION	DATE	DESCRIPTION
V1.0	03/05/2024	First version of protocol submitted to EMA
V2.0	04/06/2024	Archiving version submitted to EMA
V2.1	11/07/2024	Final version uploaded in the HMA-EMA Catalogue

	D2.2.3 - Study Protocol for P3-C1-005	
	Author(s): [name] [name]	Version: V2.1
	Dissemination level: Public	

Study Title	DARWIN EU® - Characterising interstitial lung disease in Europe
Protocol version identifier	2.1
Date of last version of protocol	11/07/2024
EU PAS register number	EUPAS1000000172
Active substance	None
Medicinal product	None
Research question and objectives	
 
1. To measure the incidence of newly diagnosed Interstitial Lung Disease (ILD) across different European countries, overall and stratified by risk factors such as age, sex and calendar time. The incidence will be assessed for the overall group of ILD as well as for the following subtypes of ILD: alveolitis/pneumonitis (excluding aspiration and infectious pneumonitis), lung fibrosis and drug induced ILD.
 
2. To describe the characteristics of patients diagnosed with ILD in 4 European countries. Characteristics include demographics, most common comorbidities, prespecified risk factors and treatments taken before diagnosis. Characteristics will be assessed for the overall group of ILD as well as for the following subtypes of ILD: alveolitis/pneumonitis (excluding aspiration and infectious pneumonitis), lung fibrosis and drug induced ILD
 
3. To measure survival rates in patients diagnosed with ILD across different European countries overall and stratified by risk factors such as age, sex and calendar time. Survival rates will be assessed for the overall group of ILD as well as for the following subtypes of ILD: alveolitis/pneumonitis (excluding aspiration and infectious pneumonitis), lung fibrosis and drug induced ILD
 

Country(ies) of study	Spain, United Kingdom, France and Germany
Author	[name] [contact] [name] [contact]

	D2.2.3 - Study Protocol for P3-C1-005	
	Author(s): [name] [name]	Version: V2.1
	Dissemination level: Public	

## LIST OF ABBREVIATIONS

Acronyms/term	Description
CDM	Common Data Model
CC	Coordinating centre
DA	Disease Analyzer
DARWIN EU®	Data Analysis and Real-World Interrogation Network
DRE	Digital Research Environment
DI-ILD	Drug-induced interstitial lung disease
DQD	Data Quality Dashboard
EEA	European Economic Area
EHR	Electronic Health Records
EMA	European Medicines Agency
ED	Emergency department
EU	European Union
GDPR	General Data Protection Regulation
ICD	International Classification of Diseases
ID	Index date
ILD	Interstitial lung disease
IP	Inpatient
IMI	Immune checkpoint inhibitors
LPD	Longitudinal Patient Database
MA	Marketing Authorisation
mTOR	Mammalian target of rapamycin
OHDSI	Observational Health Data Sciences and Informatics
OMOP	Observational Medical Outcomes Partnership
OP	Outpatient
SD	Standard deviation
SNOMED	Systematized Nomenclature of Medicine
TKI	Tyrosine kinase inhibitors
TNF	Tumour necrosis factor
WHO	World Health Organisation

	D2.2.3 - Study Protocol for P3-C1-005	
	Author(s): [name] [name]	Version: V2.1
	Dissemination level: Public	

## 1. TITLE

DARWIN EU® - Characterising interstitial lung disease in Europe

### 3. ABSTRACT (STAND ALONE SUMMARY OF THE STUDY PROTOCOL)

#### Title

DARWIN EU® - Characterising interstitial lung disease in Europe

#### Rationale and background

Interstitial lung disease (ILD) is a heterogenous group of respiratory disorders affecting the interstitium of the lungs. Drug-induced ILD are adverse drug reactions from a wide range of drugs, many of which can be life-threatening diseases. Measuring the incidence of ILD and characterising its population in Europe may guide signal detection validation discussions for drug-induced ILD.

#### Research questions

What are the incidence, the characteristics and overall survival of patients diagnosed with ILD and ILD-subtypes in four European countries in the period 2010-2022?

#### Objectives

The objectives are to measure:

- (i) the incidences of ILD as well as for the following subtypes of ILD: alveolitis/pneumonitis (excluding aspiration and infectious pneumonitis), lung fibrosis and drug induced ILD. Incidences will be stratified by age, sex and calendar time
- (ii) to characterise the patients with ILD by age, sex, comorbidities and concomitant medication. This analysis will be done in the overall ILD group and in the following ILD-subtypes (alveolitis/pneumonitis (excluding aspiration and infectious pneumonitis), lung fibrosis and drug induced ILD )
- (iii) to measure the survival rates in patients diagnosed with ILD and within the following ILD-subtypes (alveolitis/pneumonitis (excluding aspiration and infectious pneumonitis), lung fibrosis and drug induced ILD. Survival rates will be stratified by age, sex and calendar time.

#### Research methods

##### Study design

Cohort study with population-level descriptive epidemiology to estimate the incidence of ILD, and patient-level characterisation to estimate the median survival time and to characterise ILD patients by prior comorbidities and drugs used.

##### Study Population

All patients in the databases newly diagnosed with ILD in the period 1st January 2010 to 31st December 2022 with at least 365 days of data visibility prior to the date of first ILD diagnosis (except CDWBordeaux).

##### Outcome

Death

##### Variables

*Condition of interest*

	D2.2.3 - Study Protocol for P3-C1-005	
	Author(s): [name] [name]	Version: V2.1
	Dissemination level: Public	

ILD and ILD-subtypes namely i) alveolitis/pneumonitis (excluding aspiration and infectious pneumonitis), ii) lung fibrosis and iii) drug induced ILD

#### Data sources

1. Clinical Practice Research Datalink (CPRD) GOLD, United Kingdom
2. Base de datos para la Investigacion Farmacoepidemiologica en el Ambito Publico (BIFAP), Spain
3. Clinical Data Warehouse (CDW) Bordeaux, France
4. IQVIA Disease Analyzer Germany (IQVIA DA Germany), Germany

#### Sample size

Based on a preliminary feasibility assessment, the expected number of record counts for the selected condition of interest (i.e. ILD) ranged from 3,900 (CDWBordeaux) to 8,800 (IQVIA DA Germany).

#### Analysis

Calculation of the incidence of ILD and ILD subtypes by means of the *IncidencePrevalence* R package which will be stratified by age, sex and calendar year. Characterisation of patients newly diagnosed with ILD and for the ILD subtypes of interest (see above) using the *CohortCharacteristics* and *CohortDiagnostics* R packages and finally calculating the survival rates in patients with newly diagnosed ILD. This analysis will also be repeated in individuals from the respective ILD subtypes of interest (see above)

## 4. AMENDMENTS AND UPDATES

NUMBER	DATE	SECTION OF STUDY PROTOCOL	AMENDMENT OR UPDATE	REASON

## 5. MILESTONES

Additional study specific deliverables (e.g. results of validation of new disease concepts, statistical analysis plan, etc.) might be requested but this will be on an individual basis.

	D2.2.3 - Study Protocol for P3-C1-005	
	Author(s): [name] [name]	Version: V2.1
	Dissemination level: Public	

STUDY SPECIFIC DELIVERABLE	Estimative TIMELINE
Draft Study Protocol	3 rd May 2024
Final Study Protocol	4th of June
Creation of Analytical code	June 2024
Execution of Analytical Code on the data	June 2024
Interim Study Report (if applicable)	NA
Draft Study Report	30 th July 2024
Final Study Report	TBD

TBD=To be determined

## 6. RATIONALE AND BACKGROUND

Interstitial lung disease (ILD) describes a heterogeneous group of respiratory disorders affecting the interstitium of the lungs. (Kaul, Cottin et al. 2021) ILD encompasses many different pathological processes including drug-induced ILDs. (Spagnolo, Bonniaud et al. 2022) Drug-induced interstitial lung disease (DI-ILD) is also a large and very heterogeneous group of adverse drug reactions, ranging from mild to progressive and life-threatening disease. The number of drugs associated with the development of ILD continues to rise, mainly due to the use of novel monoclonal antibodies and biologics for neoplastic and rheumatologic diseases, many of which are associated with lung toxicity, and includes, among others, chemotherapeutics, molecular targeting agents, immune checkpoint inhibitors, antibiotics, antiarrhythmics, and conventional or biologic disease-modifying antirheumatic drugs. (Paolo, Philippe et al. 2022)

There is a geographical variation in the reporting of ILD as an adverse drug reaction in spontaneous case reports, with cases from Japan being more frequently reported. (Pinheiro, Blake et al. 2016, Kaul, Cottin et al. 2021) The assessment of spontaneous case reports requires knowledge of patient characteristics that commonly co-occur with either the disease or the suspected reaction in order to make an informed assessment as to whether such occurrences are drug induced or may simply be due to confounding factors.

A better understanding of the population diagnosed with ILD in Europe and its incidence (including characterising comorbidities, risk factors, medications administered around diagnosis date) may guide signal detection validation discussions for drug-induced ILD within the regulatory network. The EMA has already performed in-house study measuring the incidence of ILD in the IMRD UK, IQVIA France and IQVIA Germany databases (EUPAS50623). (De Jong 2023) This study also included ILD-subtypes allocated by aligned code groups (e.g. codes representing pneumonitis, codes representing pulmonary fibrosis) that may vary in either incidence or recording, and which could also be relevant for patient characterisation. In performing disease epidemiology and patient characterisation study of ILD and ILD-subtypes in Europe, signal detection and validation for potential drug-induced ILD will be better guided.

## 7. RESEARCH QUESTION AND OBJECTIVES

	D2.2.3 - Study Protocol for P3-C1-005	
	Author(s): [name] [name]	Version: V2.1
	Dissemination level: Public	

### Research questions

What was the incidence, what were the characteristics and what was the overall survival of patients newly diagnosed with ILD in four European countries in the period 2010-2022. These research questions are explored in the whole population of individuals newly diagnosed with ILD as well as for the two most common ILD subtypes (alveolitis/pneumonitis and lung fibrosis)

### Objectives

**Objective 1:** to measure the incidences of ILD and the incidence of ILD subtypes (alveolitis/pneumonitis excluding aspiration and infectious pneumonitis), lung fibrosis and drug induced ILD), stratified by age, sex and calendar time.

**Objective 2:** to characterise the patients with ILD by age, sex, comorbidities and concomitant medication. This analysis will be done for the overall ILD group and for the following ILD-subtypes (alveolitis/pneumonitis excluding aspiration and infectious pneumonitis), lung fibrosis and drug induced ILD).

**Objective 3:** to measure the survival rates in patients diagnosed with ILD and to measure survival rates within the following ILD-subtypes (alveolitis/pneumonitis (excluding aspiration and infectious pneumonitis), lung fibrosis and drug induced ILD). Survival rates will be stratified by age, sex and calendar time

Description of the proposed objectives to be achieved in the study is displayed in **Table 1**.

**Table 1. Primary and secondary research questions and objective.**

#### **A. Primary research question and objective.**

Objective:	
Objective 1: To measure the incidence of diagnosed ILD in four European countries, overall and stratified by age, sex and calendar time. This analysis will be repeated for the following ILD subtypes: alveolitis/pneumonitis (excluding aspiration and infectious pneumonitis), lung fibrosis and drug induced ILD).
 
Objective 2: To describe the characteristics of patients diagnosed with ILD in four European countries in terms of demographics (age and sex), comorbidities, and medications used in the one year prior to diagnosis. This analysis will be repeated for the following ILD subtypes: alveolitis/pneumonitis (excluding aspiration and infectious pneumonitis), lung fibrosis and drug induced ILD).
 
Objective 3: To measure survival rates in patients diagnosed with ILD in four European countries overall and stratified by age, sex and calendar time. This analysis will be repeated for the following ILD subtypes: alveolitis/pneumonitis (excluding aspiration and infectious pneumonitis), lung fibrosis and drug induced ILD).

Hypothesis:	Not applicable
Population (mention key inclusion-exclusion criteria):	All patients should be present in the databases with at least 365 days of prior history (except for CDWBordeaux) and be newly diagnosed with ILD (i.e. no prior diagnosis of ILD).
Exposure:	None

	D2.2.3 - Study Protocol for P3-C1-005	
	Author(s): [name] [name]	Version: V2.1
	Dissemination level: Public	

Comparator:	None
Outcome:	Overall survival (objective 3)
Time (when follow up begins and ends):	Follow-up starts after study start date (1st January 2010) or on the date where there is 1 year of prior history. (one year of history not needed for CDWBordeaux) whatever comes last. For objective 2 and 3, the follow-up starts upon the first diagnosis of ILD. The End of follow-up will be defined as the earliest of loss to follow-up, end of data availability, death, or end of study period (31st of December 2022), whatever comes first.
Setting:	Primary care data (CPRD GOLD, BIFAP, IQVIA DA Germany) and secondary care data (CDW Bordeaux).
Main measure of effect:	
Incidence rates, expressed as number of individuals newly diagnosed with ILD per 100,000 person-years. Incidence rates will be calculated overall and stratified by sex, age (age category) and calendar time (year). Incidence rates will be calculated for ILD overall and for the following ILD subtypes: alveolitis/pneumonitis (excluding aspiration and infectious pneumonitis), lung fibrosis and drug induced ILD.
 
Median survival time in patients with newly diagnosed ILD stratified by sex, age-category, and calendar time. If numbers are sufficient, survival rates will not only be done for the overall group but also for the following ILD subtypes: alveolitis/pneumonitis (excluding aspiration and infectious pneumonitis), lung fibrosis and drug induced ILD.

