#### Covariates for the patient-level characterisation study

As part of patient-level characterisation study, comorbidities will be measured in the period of 365 days prior to the index date (i.e. date of diagnosis of ILD). Concomitant medications will be measured within 30 and 365 days prior to the index date and reported for both time periods.

Covariates used to describe Patient characterisation consist of the following:

- Sex
- Age at index date (i.e. date of diagnosis of ILD). Age will be presented in age categories namely:
  - <18
  - 18-39
  - 40-59
  - 60-79
  - >=80 years.
- ILD subtypes:
  - alveolitis/pneumonitis (excluding aspiration and infectious pneumonitis)
  - lung fibrosis
  - drug-induced

	D2.2.3 - Study Protocol for P3-C1-005	
	Author(s): [name] [name]	Version: V2.1
	Dissemination level: Public	

- Unspecified ILD
- description of the top 10 of the most frequent comorbidities and concomitant medications using large-scale characterisation, as specified in the CohortCharacteristics R package and assessed in the period of 365 days prior to the index date.
- Comorbidities of interest (Gaillet, Favelle et al. 2015, Choi, Dauti et al. 2018, Joy, Arbiv et al. 2023), in particular:
  - COPD/emphysema
  - Connective tissue disease namely rheumatoid arthritis, sclerodermia, systemic lupus erythematosus (SLE), polymyositis/dermatomyositis, granulomatosis with polyangiitis (GPA)
  - GERD
  - Hepatitis B/C
  - Cancer excluding non-melanoma skin cancer
- Use of concomitant medication (assessed in the 30 days and 365 days prior to the index date) in particular:
  - chemotherapy
  - amiodarone
  - immune checkpoint inhibitors (ICIs)
  - tyrosine kinase inhibitors (TKIs including crizotinib, EGFR inhibitors, erlotinib, gefitinib)
  - mammalian target rapamycin (mTOR) inhibitors
  - rituximab
  - statins
  - methotrexate
  - nitrofurantoin
  - tumor necrosis factor (TNF)- $\alpha$  antagonists (Paolo, Philippe et al. 2022).

The operational definition of the covariates is described in [Table 7](#). Index date is the start of the incident ILD diagnosis during the study period. The preliminary concepts for prespecified conditions and drugs of interest are described in [Appendix I](#).

	D2.2.3 - Study Protocol for P3-C1-005	
	Author(s): [name] [name]	Version: V2.1
	Dissemination level: Public	

**Table 7.** Operational Definitions of Covariates.

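### Objective 2 describes comorbidities and drugs before ILD diagnosis, but every look-back window in Table 7 includes the diagnosis date, so the index ILD code and same-day drugs count as prior

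*Protocol*

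**What the plan says.** Several places set the time frame of Objective 2 before diagnosis:

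- Title table, objective 2: "prespecified risk factors and treatments taken before diagnosis".
- Abstract, study design: "to characterise ILD patients by prior comorbidities and drugs used".
- Section 7, Table 1, Objective 2: "comorbidities, and medications used in the one year prior to diagnosis".
- Section 8.6.3, comorbidities: "comorbidities will be measured in the period of 365 days prior to the index date (i.e. date of diagnosis of ILD".
- Section 8.6.3, drugs: "Concomitant medications will be measured within 30 and 365 days prior to the index date and reported for both time periods".
- Section 8.6.3 also plans a "description of the top 10 of the most frequent comorbidities and concomitant medications using large-scale characterisation", again over the 365 days before the index date.
- Section 8.8.3, Objective 2, refers to treatments before diagnosis.

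Section 8.6.3 fixes day 0: "Index date is the start of the incident ILD diagnosis during the study period". Table 7 then gives the assessment windows: [-365, 0] for large-scale characterisation, [-365, 0] for specified comorbidities, and [-30, 0] and [-365, 0] for specified drugs. In Table 5, the prior-history window is [-365, -1] and the ILD washout is [-inf, -1].

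**The concern.** A programmer works from the operational table, and there the diagnosis date lies inside every look-back window. Two things follow.

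First, large-scale characterisation counts SNOMED conditions without a prespecified list. Each patient enters the cohort through an ILD record on day 0, so that record falls in the window labelled comorbidity. The protocol does not remove ILD concepts from the ranking.

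Second, a drug or condition first recorded at the diagnostic contact is scored as present before ILD. Section 6 says the study should help assessors judge whether a reported ILD is drug-induced or explained by other factors. For that use, the order of drug and diagnosis is the essential information. The 30-day window lies inside the 365-day window and both contain day 0, so no drug row is free of same-day records.

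**Working it through.** There is no planned figure to reproduce, because section 8.7 states that no sample size was calculated. The check is a comparison of windows, followed by what the feasibility counts can and cannot show.

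**1. Windows side by side**

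| Item | Text (Table 1, 8.6.3) | Table 7 |
|---|---|---|
| Large-scale characterisation | 365 days before index | [-365, 0] |
| Specified comorbidities | 365 days before index | [-365, 0] |
| Specified drugs | 30 and 365 days before index | [-30, 0], [-365, 0] |

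**2. ILD codes in the large-scale window, overall ILD cohort**

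- Window ending at day 0: every patient has an ILD code on day 0, so the share is 100%.
- Window ending at day -1: the washout [-inf, -1] bars any earlier ILD code, so the share is 0%.

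The whole ILD content of that list therefore comes from including day 0.

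**3. How concentrated the ILD codes are**

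Inputs are the Table S2 counts for concepts included in Table S1.A. Share = concept count / sum of the included counts in that database.

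| Database | Largest concept, all included | Largest, without pneumonitis due to inhaled substance |
|---|---|---|
| BIFAP | 49,500/86,000 = 57.6% | 10,600/36,500 = 29.0% |
| CDW Bordeaux | 12,200/16,600 = 73.5% | 3,900/4,400 = 88.6% |
| CPRD GOLD | 7,300/28,000 = 26.1% | 7,300/27,500 = 26.5% |
| IQVIA DA Germany | 12,400/28,700 = 43.2% | 8,800/16,300 = 54.0% |

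Within the lung fibrosis subtype, two concepts account for 10,600/20,100 = 52.7% and 9,100/20,100 = 45.3% in BIFAP, and for 7,300/12,800 = 57.0% and 4,300/12,800 = 33.6% in CPRD GOLD.

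These shares are only indicative. The counts are rounded, may overlap between concepts and are not restricted to index codes. The footnote to Table 3 also describes the 3,900 to 8,800 counts as ILD overall, whereas Table S2 lists them as one concept. The shares make it very likely that at least one ILD concept ranks in the top 10. They do not give a number of places, because that depends on the frequencies of the competing non-ILD conditions, which the protocol does not report.

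**4. Direction of the drug effect**

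Let p be the share with a record in the window up to day -1, and q the share of the remainder with a first in-window record on day 0. Reported use = p + (1-p)q.

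- The added term (1-p)q is never negative, so the effect is upward. It is at most q.
- The relative excess is (1-p)q/p. The patients without a record in [-30, -1] include all those without one in [-365, -1]. The added term is therefore at least as large in the 30-day window and p is no larger, so the relative excess is at least as large there.
- The documents give neither p nor q. As an assumption only, p = 2% with q = 0.5%, 1% or 2% gives 2.49%, 2.98% or 3.96%. The relative excess of 24.5%, 49% or 98% mainly reflects the chosen ratio q/p and is not an estimate for this study.

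**The case against.** Day 0 may have been intended. Section 6 speaks of drugs given around the diagnosis date, the word concomitant recurs, and section 8.8.5 heads its paragraph as characteristics on the index date. This stands as a possible intention, but it does not reconcile Table 7 with Objective 2 or section 8.6.3. If day 0 was meant, the objective and the text are wrong instead.

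The contrast with Table 5 is weak evidence. An ILD washout has to stop at day -1, and the history rule concerns eligibility. This is fair: Table 5 shows that the notation can separate the two cases, not how covariate windows must close.

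The outputs listed in section 8.8.5 cover prespecified comorbidities and drugs, deaths and survival curves. The top-10 ranking appears only in section 8.6.3, and an ILD code in it would be easy to spot. This stands. A reader might infer that the main baseline table is filled with the index disease, but its prespecified comorbidities contain no ILD code.

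A day-0 record may be a repeat prescription. Section 11 also says that some hospital-administered drugs related to ILD are not routinely captured in the primary care databases. Both points limit how much of the day-0 signal is a response to the diagnosis, and they leave its size unknown.

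CDWBordeaux has no prior-history requirement, so a window ending at day -1 could miss existing drugs and conditions there. This is a real cost of simply dropping day 0. A separate day-0 column meets it, because no record is lost.

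Some of this may be left to package settings (section 8.8.4) or to an analysis plan not shown. However, the windows themselves are fixed in this protocol, and fixed inconsistently.

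**Conclusion.** The inconsistency is in the current text and should be corrected. Under Table 7 as written, all patients carry an ILD code in the large-scale comorbidity window, against none in the overall ILD cohort if the window ended at day -1. ILD concepts are very likely to appear in the top-10 list, assuming the code does not drop index concepts, which the protocol does not say. Drugs and conditions first recorded on the diagnosis day count as prior. For drugs the effect is upward, relatively at least as large in the 30-day window, and of unknown size.

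A reader might go further and conclude that a set number of the ten places will be ILD, or that prior drug use will be overstated by a given percentage. The documents support neither: the first needs the frequencies of other conditions, and the second needs day-0 prescribing rates. Whether drug windows should be nested or disjoint is a reporting preference and not part of this point.

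**What to change.** In Table 7, end the large-scale characterisation and comorbidity windows at day -1, as [-365, -1], and the drug windows likewise, as [-30, -1] and [-365, -1]. Add a separate [0, 0] column so that same-day records are kept but not called prior. This matters most for CDWBordeaux. Exclude the Table S1.A concepts from the top-10 comorbidity ranking. The exclusion is still needed after the window change if subtype cohorts can carry an earlier code of another ILD subtype. Objective 2 and section 8.6.3 can then stay as worded.

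The cost is a change of window parameters, one extra output column and an edit to Table 7. The small downside is that existing medication or comorbidity first recorded at the index contact moves to the day-0 column.
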